9.5.7 Neurological Examination

Elements of the neurological examination may include inspection for tremor, extraocular movements, brachial and patellar deep tendon reflexes, finger-nose pointing, and Romberg sign.

The below table presents the scoring of the neurological examination findings. For subjects with mild (1+) tremor or nystagmus at baseline, increases in these findings should not be scored at a higher level unless the examiner judges them to be significantly exacerbated compared to baseline.

Score	0	1	2	3	4
Tremor	Absent	Visible with limb extension and/or careful inspection	Visible without limb extension.	Interferes with motor function	
Nystagmus	Absent	1 to 3 beats on lateral gaze	>3 beats on lateral gaze	Present on forward gaze	
Reflexes (brachial or patellar)	Normal	Trace	Absent	Increased	Clonic
Finger-nose	Normal	Abnormal			
Romberg sign	Absent	Present			

The frequency of neurological survey data will be summarized by part, treatment and timepoint, and listed.

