7.4.1. Dose Decision/Escalation

By nature of being a dose-escalation study, data will be evaluated on an ongoing basis until the maximum tolerated dose (MTD) is determined or the highest planned dose is administered. The highest dose level that is tolerated will be designated as the MTD.

Safety data will be the primary criteria for the dose escalation. In addition, if available at the time of the dose-escalation decision, PK results will be used as supporting data. No dose escalation can occur without prior discussion and agreement between the investigator and the Lilly study team. See Sections 5.1.1 and 5.1.3 for further details.

Safety data, in particular AEs, SAEs, BP, PR, and adverse laboratory abnormalities, will be independently assessed by the investigator and will be considered related to the investigational medicinal product, unless there is clear evidence that the event is not related.

If any of the following scenarios occur, dosing at the current level and further dose escalation will be discontinued:

- 1) a single subject experiences an SAE that is related to LY3154885 administration
- 2) 2 subjects experience a clinically significant event of persistent tremors that is deemed to be related to LY3154885 administration
- 3) 2 subjects experience clinically significant increases in scheduled vital signs that are deemed to be related to LY3154885 administration
- 4) 2 or more subjects at 1 dose level experience other moderate or severe treatment-related AEs that impair normal activities and are deemed to be related to LY3154885 administration

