9.4.5. Neurological Examination

A directed neurological examination will be performed by the investigator (or designee) at the time points specified in the Schedule of Activities (Section 2). If clinically significant abnormalities are noted at these time points, additional examinations should be performed as clinically necessary. Examination procedures may include inspection for tremor, extraocular movements, brachial and patellar deep tendon reflexes, finger-nose pointing, and Romberg sign.

Table HUAA.9.1 presents the scoring of neurological examination findings.

Table HUAA.9.1. Scoring of Neurological Examination Findings

Score	0	1	2	3	4
Tremor	Absent	Visible with limb extension and/or careful inspection	Visible without limb extension	Interferes with motor function	
Nystagmus	Absent	1 to 3 beats on lateral gaze	>3 beats on lateral gaze	Present on forward gaze	
Reflexes (brachial or patellar)	Absent	Trace	Normal	Increased	Clonic
Finger-nose	Normal	Abnormal			
Romberg sign	Absent	Present			

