11. CHANGES FROM THE PROTOCOL SPECIFIED STATISTICAL ANALYSES

There were no changes from the protocol specified statistical analyses.

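### SAP 9.5.7 adds a baseline-dependent scoring exception for tremor and nystagmus that the protocol scale lacks, so the same finding can be recorded with different scores

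*SAP*

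**What the plan says.** Protocol 9.4.5 states that "Table HUAA.9.1 presents the scoring of neurological examination findings". For tremor and nystagmus that table runs from 0 to 3, each level tied to something the examiner can observe. Neither the table nor the text around it refers to the subject's baseline. Clinical significance appears in that section only as a trigger for repeat examinations: "If clinically significant abnormalities are noted at these time points, additional examinations should be performed as clinically necessary".

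SAP 9.5.7 prints the same tremor and nystagmus anchors with an added rule. "For subjects with mild (1+) tremor or nystagmus at baseline", it says, "increases in these findings should not be scored at a higher level unless the examiner judges them to be significantly exacerbated compared to baseline". It does not define how much worsening counts as significant, or which examination is the baseline.

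The planned output is descriptive: "The frequency of neurological survey data will be summarized by part, treatment and timepoint, and listed". No shift or change from baseline is planned for these scores. SAP Section 11 states: "There were no changes from the protocol specified statistical analyses".

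**The concern.** One scale has two scoring conventions. Under the protocol, a score describes what was seen. Under the SAP, it also depends on where the subject started and on a judgement with no stated threshold. The exception works only toward no change.

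The rule also sits where it cannot be applied reliably. Examiners work from the protocol, which does not contain it. Analysts work from the SAP but cannot apply it afterwards, because it needs the examiner's judgement at the bedside. Nothing in the planned tables would show which convention produced a given score.

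At stake is the readability of one safety measure. Safety and tolerability is the primary objective of this first-in-human study, and the protocol describes central nervous system effects in the nonclinical studies as monitorable. With 8 or 9 active subjects per dose level, a single unrecorded shift is visible in a frequency table.

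**Working it through.** The documents give no figure to reproduce. The check is a comparison of the two sections, followed by a labelled illustration of size.

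**Step 1. Score given to one fixed postdose finding.** Take a finding that meets anchor 2, such as a tremor seen without the limb being held out.

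| Baseline score | Examiner judges it significantly worse | Protocol score | SAP score |
|---|---|---|---|
| 0 | yes or no | 2 | 2 |
| 1 | yes | 2 | 2 |
| 1 | no | 2 | 1 |
| 2 | yes or no | 2 | 2 |

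The conventions differ in one row only: baseline 1 with an increase not judged significant. There, a rise from 1 to 2 is recorded as no change.

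**Step 2. Is this a version difference?** SAP Section 3 says it was written from the May 2019 protocol and amendment (a). The visible text of the Amendment (b) summary (protocol Appendix 6) lists no change to the neurological examination section. Amendment (b) therefore does not explain the mismatch. SAP Section 3 also says that the SAP supersedes the protocol's statistical considerations; that does not extend to examination procedures.

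**Step 3. Which baseline?** SAP 9.5.3 and 9.5.4 define baseline as Day 1 predose for laboratory values and vital signs. Section 9.5.7 defines none, although the schedules include a screening examination and predose examinations, and Part A has three periods.

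**Step 4. Size.** Protocol 5.1.1 intends 8 active subjects per dose level in Part A; 5.1.3 plans 9 in Part C. One subject is 1/8 = 12.5% or 1/9 = 11.1%.

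The number affected depends on three rates that the documents do not give: the share b at baseline 1, the share w of those who rise a category, and the share s of those rises not judged significant. Expected unrecorded increases per dose level are n × b × w × s, and the chance of at least one is 1 − (1 − b × w × s)^n. With assumed ranges b = 5% to 30% and w = 20% to 50%, and s assumed to be 50%:

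- n = 8, low end: 8 × 0.05 × 0.2 × 0.5 = 0.04; chance of at least one 4%.
- n = 8, high end: 8 × 0.30 × 0.5 × 0.5 = 0.60; chance 46%.
- n = 9, low end: 9 × 0.05 × 0.2 × 0.5 = 0.045; chance 4%.
- n = 9, high end: 9 × 0.30 × 0.5 × 0.5 = 0.675; chance 50%.

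These figures show only that the answer runs from negligible to about an even chance per dose level. They are not estimates for this trial.

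**Step 5. The rest of the table.** Reflexes are coded Absent 0, Trace 1, Normal 2 in the protocol, but Normal 0, Trace 1, Absent 2 in the SAP. A normal reflex is 2 in one document and 0 in the other, for every subject.

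**The case against.** A reader might infer that treatment-emergent worsening as such is suppressed. The documents do not support that. SAP 9.5.1 counts as treatment-emergent any adverse event that was present before dosing and grows more severe afterwards, with no significance threshold. The primary endpoint does not pass through the score. One worsening could be a treatment-emergent event while the score stays the same.

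A reader might also infer that the tremor stopping criterion is weakened. Protocol 7.4.1 rests that criterion on whether "2 subjects experience a clinically significant event of persistent tremors" judged related to treatment. It cites neither the score nor Table HUAA.9.1. The safety data named for escalation reviews in 5.1.1 and 5.1.3 do not mention neurological scores.

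Three further points stand. If examiners follow only the protocol, the SAP sentence has no effect. Predose is a scheduled neurological time point in every part, so pre-existing scores of 1 will show in the predose rows and in the listings; it does not follow that the table overstates background findings. Parts A to C are investigator-blind, so the rule would be applied without knowledge of allocation. If the drug does worsen tremor, however, more increases could be held back on active treatment than on placebo.

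The statement in SAP Section 11 carries little weight here. It concerns analyses, and the protocol specifies no analysis of these scores.

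None of this removes the conflict. The two sections still prescribe different scores for the same finding.

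**Conclusion.** The point holds as a scoring conflict that should be reconciled. The same postdose tremor or nystagmus can receive different scores, some one-category increases can go unrecorded in the neurological score tables, and a reader of those tables could not tell which convention was used.

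Its reach is limited to subjects at 1+ at baseline and to increases the examiner does not judge significant. The adverse event endpoint and the stopping criterion are unaffected. The number of subjects is unknown: the range in the working rests wholly on assumed rates. The existence of the conflict needs no assumption, and neither does the difference in reflex coding.

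**What to change.** - Remove the baseline-dependent sentence from SAP 9.5.7, so that recorded scores follow the anchors in protocol Table HUAA.9.1 at every examination. Confirm that no site scoring instruction carries the sentence.
- Handle pre-existing mild signs in the analysis. Alongside the planned frequencies, add a shift table by treatment for tremor and nystagmus, from the predose score to the worst postdose score. Define predose as the same dosing day in the single-dose parts and as Day 1 predose in Part C.
- Reconcile the reflex coding so that both documents use one set of codes.

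The cost is an SAP wording change and one more table. The predose examinations it needs are already scheduled. The downside is that a few more one-point shifts will be reported, in all arms.

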	Screening	Periods 1, 2, and 3					ED	Follow-up	Comments
Procedure	-28 to -3 days prior to dosing in Period 1	Day -2	Day -1	Day 1	Day 2	Day 3		At least 7 days after final dose	
Informed consent	X								
Admission to CRU		X (Period 1)	X (Periods 2&3)						
Discharge from CRU						X			
Medical history	X								
AE/medication review			X	X	X	X	X		
Height/weight	X						X	X	Height at screening only.
Neurological exam (hours)	X			Predose, 4, 8	24	48	X	X	
LY3154885/Placebo administration (hours)				0					
Vital signs (BP, PR [supine], temperature) (hours)	X		X	Predose, 2, 4, 8, 12	24, 36	48	X	X	Time points may be added for each study period, if clinically indicated. On Day 1, temperature will be measured at predose only.
ABPM			X	X	X				The ABPM on Day -1 is a 24-hour collection in Period 1 only (baseline measurement). See Section 9.4.4.
Clinical laboratory tests	X	X		Predose		X	X	X	See Appendix 2, Clinical Laboratory Tests, for details. PI must review the result of Day-2 results prior to Day 1 dose in Period 1 only.
Pregnancy test	X	X					X	X	Serum test at screening and admission of Period 1 only; urine test at all other time points.
PE/MA	X			Predose			X	X	Full PE/MA at screening and prior to final discharge from the study. Symptom-directed PE/MA at all other time points and as deemed necessary by the investigator.

continued

Study Schedule Protocol J1Z-MC-HUAA (Part A: Single-Ascending Dose – 3 Study Periods) (concluded)

	Screening	Periods 1, 2, and 3					ED	Follow-up	Comments
Procedure	-28 to -3 days prior to Period 1	Day -2	Day -1	Day 1	Day 2	Day 3		At least 7 days after final dose	
Single safety 12-lead ECG (hours)	X			Predose, 2, 4	24	48	X	X	
PK sampling (hours)				Predose, 0.5, 1, 2, 3, 4, 5, 6, 8, 12	24, 36	48			Sampling times are relative to the time of study treatment administration (0 hour).
Stored non-PGx plasma sample (hours)				Predose, 8	24				Stored sample for biomarker research. Sampling times are relative to the time of study treatment administration (0 hour).
PGx sample			X						Single sample for pharmacogenetic analysis taken prior to/on Day 1 of Period 1.
Urine collection (hours)				0-12, 12-24	24-36				Urine collection time starts from actual dosing time on Day 1 and finishes within \pm 30 minutes of the 36-hour time point.
Serum creatinine				Predose					To be collected at predose and sent to central laboratory.

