3. INTRODUCTION

This SAP has been developed after review of the Clinical Study Protocol (final version dated 07 May 2019) and amendment (a) (dated 21 June 2019).

This SAP describes the planned analysis of the safety, tolerability, pharmacokinetic (PK) and pharmacodynamic (PD) data from this study. A detailed description of the planned TFLs to be presented in the clinical study report (CSR) is provided in the accompanying TFL shell document.

The intent of this document is to provide guidance for the statistical and PK analyses of data. In general, the analyses are based on information from the protocol, unless they have been modified by agreement between Eli Lilly and Company and Covance Early Clinical (EC) Biometrics. A limited amount of information concerning this study (e.g., objectives, study design) is given to help the reader's interpretation. This SAP must be signed off prior to first subject administration of study drug for this study. When the SAP and TFL shells are agreed upon and finalized, they will serve as the template for this study's CSR.

This SAP supersedes the statistical considerations identified in the protocol; where considerations are substantially different, they will be so identified. If additional analyses are required to supplement the planned analyses described in this SAP, they may be performed and will be identified in the CSR. Any substantial deviations from this SAP will be agreed upon between Eli Lilly and Company and Covance EC Biometrics and identified in the CSR. Any minor deviations from the TFLs may not be documented in the CSR.

This SAP is written with consideration of the recommendations outlined in the International Conference on Harmonisation (ICH) E9 Guideline entitled Guidance for Industry: Statistical Principles for Clinical Trials¹ and the ICH E3 Guideline entitled Guidance for Industry: Structure and Content of Clinical Study Reports².

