9. STATISTICAL METHODOLOGY

9.1 General

Data listings will be provided for all data that is databased. Summary statistics and statistical analysis will only be presented for data where detailed in this SAP. For continuous data, summary statistics will include the arithmetic mean, arithmetic standard deviation (SD), median, min, max and N; for log-normal data (e.g. the PK parameters) the geometric mean and geometric coefficient of variation (CV%) will also be presented. For categorical data, frequency count and percentages will be presented. Data listings will be provided for all subjects up to the point of withdrawal, with any subjects excluded from the relevant population highlighted. Summary statistics and statistical analyses will generally only be performed for subjects included in the relevant analysis population. For the calculation of summary statistics and statistical analysis, unrounded data will be used.

Mean change from baseline is the mean of all individual subjects' change from baseline values. Each individual change from baseline will be calculated by subtracting the individual subject's baseline value from the value at the timepoint. The individual subject's change from baseline values will be used to calculate the mean change from baseline using a SAS procedure such as Proc Univariate.

Data analysis will be performed using SAS[®] Version 9.4 or greater.

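### SAP 9.5.7 exchanges reflex codes 0 and 2 relative to protocol Table HUAA.9.1 without saying so, so normal reflexes could be reported as absent and absent reflexes as normal

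*SAP*

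**What the plan says.** Protocol section 9.4.5 sets out in Table HUAA.9.1 how the findings of the directed neurological examination are scored. For scores 0 to 4 its reflex row reads "Reflexes (brachial or patellar) Absent Trace Normal Increased Clonic".

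SAP section 9.5.7 presents a table for the same purpose. Its reflex row, for the same five scores, reads "Reflexes (brachial or patellar) Normal Trace Absent Increased Clonic". The section then plans the output: "The frequency of neurological survey data will be summarized by part, treatment and timepoint, and listed". SAP section 9.1 adds the general rule: "For categorical data, frequency count and percentages will be presented".

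SAP section 3 gives the plan its authority over the report: "When the SAP and TFL shells are agreed upon and finalized, they will serve as the template" for the clinical study report. It also states that the SAP supersedes the protocol's statistical considerations and that substantial differences will be identified. Section 9.5.7 identifies none, and section 11 says: "There were no changes from the protocol specified statistical analyses".

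**The concern.** Site examiners work from the protocol, while programmers have reason to work from the SAP. With two keys in circulation, a number recorded under one can be labelled under the other. The exchanged codes are Normal and Absent, so the error would reverse the clinical meaning of the finding.

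Safety and tolerability is the primary objective, and protocol section 3.2 reports central nervous system effects in the nonclinical studies, which makes the neurological examination a relevant safety output. What is at stake is the correctness of one descriptive table and its listing. Reflex scores are not named in the dose-escalation data (protocol sections 5.1.1 and 5.1.3) or in the stopping rules (section 7.4.1), and the SAP plans no inferential safety analysis.

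**Working it through.** **Step 1. Compare the keys code by code.**

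| Score | Protocol Table HUAA.9.1 | SAP 9.5.7 | Agree? |
|---|---|---|---|
| 0 | Absent | Normal | No |
| 1 | Trace | Trace | Yes |
| 2 | Normal | Absent | No |
| 3 | Increased | Increased | Yes |
| 4 | Clonic | Clonic | Yes |

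Two of five codes differ. The rows for tremor, nystagmus, finger-nose and Romberg sign carry the same codes in both tables. Both reflex rows have all five cells and line up with their neighbours, so a fault in reading the PDF is unlikely.

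**Step 2. Decode protocol-scale scores with the SAP key.**

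| Recorded (protocol scale) | True meaning | Reported under the SAP key |
|---|---|---|
| 2 | Normal | Absent |
| 0 | Absent | Normal |
| 2 to 0 | Reflexes lost | Absent to Normal |
| 2 to 1 | Reflexes reduced | Absent to Trace |

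Decoding in the other direction gives the same exchange. Numeric shifts also differ in meaning: the protocol row rises steadily from absent to clonic, whereas the SAP row goes from normal down to absent and then jumps to increased and clonic.

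**Step 3. Could version lag explain it?** The SAP names its sources: "This SAP has been developed after review of the Clinical Study Protocol (final version dated 07 May 2019) and amendment (a"). The protocol in hand is amendment (b). Its list of changes (protocol Appendix 6) shows no edit to section 9.4.5 or Table HUAA.9.1.

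**Step 4. Count the exposure in Part A.** The neurological row of the Part A schedule reads "Neurological exam (hours) X Predose, 4, 8 24 48 X X": screening, five timepoints in each period, early discontinuation and follow-up. A completer has no early-discontinuation visit.

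- Examinations per completer: 1 + (3 periods × 5) + 1 = 17
- Planned completers: 2 cohorts × 12 = 24
- Scheduled examinations: 24 × 17 = 408

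This is an upper figure for examinations with reflex scoring, because section 9.4.5 lists reflexes among procedures that an examination may include.

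**Step 5. Mislabelled records under assumed shares.** The documents give no distribution of reflex scores, so the share carrying code 0 or 2 is assumed, with one reflex score per examination.

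| Assumed share coded 0 or 2 | Mislabelled of 408 |
|---|---|
| 80% | 0.80 × 408 ≈ 326 |
| 90% | 0.90 × 408 ≈ 367 |
| 99% | 0.99 × 408 ≈ 404 |
| CRF stores text, or the SAP key | 0 |

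Parts B to D add further examinations.

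**The case against.** The discrepancy itself cannot be argued away. The case on the other side concerns its cause, its reach and its weight.

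- **The SAP key may be deliberate.** In the SAP table, score 0 is the unremarkable category in all five rows, which is coherent. This stands as a possibility, and it is why the SAP should not be presumed to be the document in error. An intended recoding would still need to be declared and mapped from the protocol scores, and the SAP does neither.
- **Version lag is unlikely but not excluded.** The original protocol and amendment (a) are not available, and one entry in the amendment (b) summary is redacted. The SAP carries superseded text elsewhere, such as evening admission and the Day 6 safety review in Part C. This stands in part, but lag would explain the conflict with the current protocol without removing it.
- **Section 11 covers statistical analyses, and the key sits in an assessment section of the protocol.** This is fair: the section 11 statement is not plainly false on this point. The key nevertheless determines what the planned table says.
- **The damage is conditional and visible.** The CRF and shells are not in hand. A wholesale exchange would show at predose and on placebo, and might be caught when the shells or CRF are prepared. This stands and limits the severity. Nothing in the documents guarantees the catch.

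**Conclusion.** The concern holds. The protocol and the SAP give contradictory meanings to reflex codes 0 and 2, neither document resolves the conflict, and the SAP does not identify it. That much is certain from the text.

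Misreporting is a risk, not a certainty. It requires numeric scores recorded on one key and labelled with the other. If that happens, most reflex records would probably be affected: 326 to 404 of up to 408 Part A examinations if 80% to 99% carry code 0 or 2. Otherwise the number mislabelled in this way is zero. The consequence is limited to a descriptive safety table and its listing. It should be fixed, because the error would reverse the meaning of the finding and is cheap to prevent.

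**What to change.** Before programming, confirm which reflex code list the CRF and the table shells carry, and then use a single list in the protocol, CRF, SAP and shells.

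- If the CRF and shells carry the protocol list, correct two cells of the SAP 9.5.7 reflex row so that it reads 0 Absent, 1 Trace, 2 Normal, 3 Increased, 4 Clonic. The cost is two cells and one check.
- If they do not, reconcile all four documents first and record the difference from the protocol in SAP section 11. This costs more, since the protocol or CRF may need changing.

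While section 9.5.7 is open, a separate point can be settled. It contains a rule for scoring tremor and nystagmus when the baseline finding is mild, and protocol section 9.4.5 has no such rule. It affects how examiners score, so the two sections should be reconciled.

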5.5. Justification for Dose

In Part A, the planned clinical doses to be tested are 15, 45, 100, 200, 400, and 500 mg based on animal toxicology/toxicokinetics, preclinical pharmacology, and PK information. In Part B (CYP3A4 Interaction), the LY3154885 dose selection will be based on emerging data from Part A but is currently planned to be \leq 200 mg. In Part C (MAD), dose selection will be based on emerging safety, tolerability, and PK data from Part A and Part B, but Part C is currently planned to start at 35 mg and not exceed the highest dose in Part A or the maximum exposure achieved in Part A or B that are found to be well tolerated. In Part D, the dose for the capsule and tablet is planned to be \leq 400 mg but will ultimately be based on emerging safety, tolerability, and PK data from Part A.

The toxicity profile of LY3154885 has been characterized in rats and monkeys through a package of GLP compliant, repeat-dose toxicology, safety pharmacology, and genetic toxicology studies; non-GLP toxicity studies were conducted with LY3154885 as well and are discussed in the IB. These studies with LY3154885 demonstrate an acceptable safety profile for human testing with CV and CNS effects that are transient and monitorable.

CCI

CCI

(Table HUAA.5.1).

The maximum dose for this study is expected to be 500 mg based on animal toxicology studies and human PK predictions for LY3154885, CCI

CCI A 500-mg dose in humans is predicted to result in a mean plasma AUC of CCI $\mu\text{g}\cdot\text{hr}/\text{mL}$ and C_{\max} of CCI $\mu\text{g}/\text{mL}$; these values are equivalent to 1/10th the AUC at the NOAEL in monkeys and 1/10th the C_{\max} at the NOAEL in rats. The C_{\max} and AUC-based multiples associated with CCI from the non-GLP study in rats, which were not observed at similar exposures in the GLP study, are also presented in Table HUAA.5.1. To note, the predicted human C_{\max} at 500 mg is CCI below the C_{\max} at the NOEL for PPD in both rats and monkeys. Pharmacokinetic data will be reviewed during the study to support dose escalations (see Section 10.3.5 for details) and maintain predicted drug exposures below 1/10th the AUC at the NOAEL in monkeys and 1/10th the C_{\max} at the NOAEL in rats. A dose higher than 500 mg may be studied if human PK data from previous cohorts suggests the predicted exposure will be below 1/10th the AUC at the NOAEL in monkeys and 1/10th the C_{\max} at the NOAEL in rats.

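### SAP 9.5.7 gives a reflex scoring key that exchanges codes 0 and 2 (Absent and Normal) against Protocol Table HUAA.9.1 and declares no recode

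*SAP*

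**What the plan says.** Protocol 9.4.5 sets out a directed neurological examination and states: "Table HUAA.9.1 presents the scoring of neurological examination findings". Under score columns 0 to 4, the reflex row of that table is "Reflexes (brachial or patellar) Absent Trace Normal Increased Clonic".

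SAP 9.5.7 reproduces a scoring table for the same examination with the same columns 0 to 4. Its reflex row is "Reflexes (brachial or patellar) Normal Trace Absent Increased Clonic". Below the table it gives the planned output: "The frequency of neurological survey data will be summarized by part, treatment and timepoint, and listed".

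SAP 3 identifies the protocol version that the SAP was written from: "This SAP has been developed after review of the Clinical Study Protocol (final version dated 07 May 2019) and amendment (a"). It also undertakes to identify substantial differences from the protocol's statistical considerations. SAP 9.5.7 says nothing about a recoding of reflexes. The protocol supplied is amendment (b). Its summary of changes in Appendix 6 does not list Section 9.4.5 or Table HUAA.9.1.

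**The concern.** Both tables are current text and both claim to define the same collected score, yet 0 and 2 mean opposite things in them. The site works from the protocol. The SAP table is the only decoding key that the SAP gives to whoever programs the output. If the data reach the programmer as numbers, following each document faithfully produces a wrong label.

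This is a first-in-human study with safety and tolerability as the primary objective. Protocol 5.5 relies on animal findings of "CV and CNS effects that are transient and monitorable". The neurological examination is one of the places where such effects would be documented. A reflex summary in which normal reads as absent, and a true loss reads as normal, would misdescribe that item.

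**Working it through.** **Inputs.** The two reflex rows above; the planned frequency summary in SAP 9.5.7; the Part A design of 8 subjects on LY3154885 and 4 on placebo per dose session, with six planned doses (Protocol 5.1.1); and the Part A examination times of predose, 4, 8, 24 and 48 hours (Protocol Section 2). The plan states no figure to reproduce here.

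**Step 1: compare the rows.**

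| Code | Protocol Table HUAA.9.1 | SAP 9.5.7 | Agree? |
|---|---|---|---|
| 0 | Absent | Normal | No |
| 1 | Trace | Trace | Yes |
| 2 | Normal | Absent | No |
| 3 | Increased | Increased | Yes |
| 4 | Clonic | Clonic | Yes |

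Two of five reflex codes differ, and they differ by an exact exchange. The tremor, nystagmus, finger-nose and Romberg rows carry the same codes in both documents. A fault in reading the PDF is therefore unlikely. With the SAP reflex row put in protocol order, all five rows agree.

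**Step 2: follow the label through to the output.** Assume that scores are stored as numbers on the protocol key and labelled with the SAP key. Then:

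- printed Absent = number truly Normal
- printed Normal = number truly Absent
- Trace, Increased and Clonic are unchanged

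For the 8 subjects on drug at one Part A dose:

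| True Normal | True Absent | Printed Normal | Printed Absent |
|---|---|---|---|
| 8 | 0 | 0 | 8 |
| 7 | 1 | 1 | 7 |
| 6 | 2 | 2 | 6 |

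Suppose all eight are normal predose and two have lost reflexes by 4 hours. The true Absent count goes from 0/8 to 2/8. The printed count goes from 8/8 to 6/8, so the direction of change reverses.

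**Step 3: the alternative.** If reflexes are captured as text, or were scored on the SAP key from the start, the printed labels are correct and the number of mislabelled records is zero.

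**Step 4: how many records could carry the item.** Scheduled Part A examinations around dosing are 8 × 5 × 6 = 240 on drug and 4 × 5 × 6 = 120 on placebo, 360 in all. This is a ceiling for Part A, not a count of affected records, because both documents list reflexes among the elements that the examination may include. Parts B, C and D schedule the examination too.

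**The case against.** The strongest reply is that no output has been shown to be wrong. The summary sentence in SAP 9.5.7 does not say that numeric scores will be tabulated or decoded with the table above it. The layout belongs to the TFL shells, and neither those nor the CRF is among the documents. This stands: the exchange of codes is certain, but the mislabelled table is conditional.

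The SAP order may also be intended. It makes 0 the unremarkable finding in every row. That is possible, and it means the documents do not show which table is the mistaken one. It does not remove the problem, because an intended recode of a collected score needs a stated mapping, and there is none.

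Three stronger readings are tempting and are not supported:

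- **That records may be a mixture of both keys and beyond recovery.** This is a single-center study whose examiners work from the protocol. Nothing suggests that any record was scored from the SAP. The plausible failure is a uniform swap, which would show up at once, since nearly everyone would appear to lack reflexes, and relabelling would reverse it.
- **That SAP 11 makes a false statement.** It reads "There were no changes from the protocol specified statistical analyses". The protocol specifies no statistical analysis of this examination and leaves the detail of safety analyses to the SAP (Protocol 10.3.1.2), so a difference in a scoring key does not contradict that sentence.
- **That the primary safety assessment or dose decisions are compromised.** The primary endpoint is the incidence of treatment-emergent adverse events. Escalation reviews use adverse events, vital signs, ECGs and laboratory results (Protocol 5.1.1 and 5.1.3). The stopping rules in Protocol 7.4.1 name tremor but not reflexes. Examiners act on what they see at the time, not on a later frequency table.

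A version lag is another candidate explanation, since the SAP predates amendment (b). The amendment's change list does not touch this section, so it gives no support for that.

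**Conclusion.** The point holds as a conflict between two current scoring keys for one item: codes 0 and 2 are exchanged and no recode is declared. It is an incorrect or unexplained coding rule, not merely missing detail.

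Its effect on results depends on one assumption that the documents cannot settle, namely that reflexes are held as protocol-coded numbers and labelled with the SAP key. Under that assumption, every Normal and every Absent reflex in the frequency table is mislabelled, up to 8/8 at a Part A dose. If the listing prints SAP labels it has the same error; if it prints bare numbers it is ambiguous. Under text capture, no output is affected. In either case the reach is one descriptive safety item, and PK and the adverse-event endpoint are unaffected. It should be corrected because the correction is cheap, not because a conclusion of the trial depends on it.

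A separate, minor point sits in the same SAP section. For subjects with 1+ tremor or nystagmus at baseline it tells examiners that "increases in these findings should not be scored at a higher level unless the examiner judges them to be significantly exacerbated compared to baseline". Protocol 9.4.5 has no such rule, and an instruction found only in the SAP may not reach the examiners. It has no bearing on the reflex codes.

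**What to change.** Before database lock, check which reflex key the CRF carries.

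- If the site scored on the protocol table, correct the SAP 9.5.7 reflex row to 0 Absent, 1 Trace, 2 Normal, 3 Increased, 4 Clonic.
- Otherwise, state the mapping from the collected score to the reported category in the SAP.
- In either case, print the reflex category as text, not as a number, in the frequency table and the listing.

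The cost is one check against the CRF, one corrected row or one mapping statement in the SAP, and text labels in one table and one listing. No new data are needed. This route leaves the protocol alone. Changing Table HUAA.9.1 instead might require a protocol amendment, which the problem does not justify.

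The baseline tremor and nystagmus rule can be handled separately: put it in the site's examination instructions if it is meant to apply, or delete it from the SAP.
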